1. LIST OF ABBREVIATIONS

Abbreviation	Definition
EULAR	The European League Against Rheumatism
RA	Rheumatoid Arthritis
TNF	Tumor Necrosis Factor
DMARD	Disease modifying antirheumatic drug
MTX	Methotrexate
DAS	Disease Activity Score
CRP	C-reactive protein
PSM	Propensity Score Method
PS	Propensity Score
IPTW	Inverse Probability of Treatment Weighting
SMD	Standardized Mean Difference
TSQM	Treatment Satisfaction Questionnaire for Medication
QoL	Quality of Life
EQ-5D	EuroQoL-5Dimensions
EQ-VAS	EuroQoL-Visual Analogue Scale
PRO	Patient Reported Outcome

3. AMENDMENTS AND UPDATES

Amendment number	Date	Substantial or administrative amendment	Protocol section(s) changed	Summary of amendment(s)	Reason
2.0	18.05.11	Substantial	P 4, 5	2. RESPONSIBLE PARTIES PPD [REDACTED] - PPD [REDACTED] removed and PPD [REDACTED] added	PPD [REDACTED] Change in author
				6. Research Questions and Objectives 7.2.1. Inclusion Criteria - Inclusion criteria modified from more than 3 months and less than 2 years to more than 6 months and less than 2 years	Modified as subjects who have been taking tofacitinib citrate for 3 months and adalimumab for 6 months are more likely to be included in the study clinically. DAS28 from the clinical records was measured at 6 months, and this was applied.
			P 10	7.3. Variables Graph 1. Assessments [15, 20-21]: 2. Clinical characteristics - tofacitinib citrate or adalimumab added to DMARD - changed measuring units to the dose unit (mg/month)	To specify DMARD types, those in parenthesis have been added. Prescribing patterns are very different; therefore, the measuring unit was changed to include all variations.
			P 19	8.4. Ethical conduct of the study - Recent Declaration of Helsinki added	Most recent Declaration of Helsinki added
3.0	2019.01.31	Substantial	P 5	2. RESPONSIBLE PARTIES PPD [REDACTED] [REDACTED] 7.6.2. Data Collection Method - according to the included institutions, the number of institutions was changed to 23	According to the institutions added

<A3921304>NON-INTERVENTIONAL STUDY PROTOCOL
 <Version3.2>,<10 December 2019>

			P 6 P 17	4. Milestones - End date of data collection changed to Sep 30, 2019 7.6.2. Data Collection Method - Data collected dates changed to September 30, 2019.	Followed data collection extension
			P 9-11	7.2.2. Exclusion criteria - Modified and added 7.3. Variables Graph 1. Assessments [15, 20-21]: 2. Clinical characteristics	Followed physician's advice that csDMARDs co-administered with bDMARDs can include items other than MTX and that there are no differences between csDMARD types.
			P 6, 14, 18	3. Amendments and Updates - reason for ver 2.0 modification: ~ patients who have been taking tofacitinib citrate for 3 months ~ 7.4 Data Sources - patients through a chart review and subject questionnaires 7.7.1 Outcome Comparisons Using PSMs - when the assumption for the parametric hypothesis is not satisfied- ~ when the assumptions for parametric hypothesis is not satisfied, non-parametric~	Changed to more appropriate term, and errors corrected.
			P 20	8. Study subject protection	Pfizer protocol template CCI [REDACTED]
3.1	2019.09.02	Administrative	P 9 P 18	4. Milestones - End date of data collection changed to December 31, 2019. 7.6.2. Data Collection Method - Data collected dates changed to December 31, 2019.	Followed data collection extension
3.2	2019.12.10	Administrative	P 9 P 18	4. Milestones	Followed data collection extension

				
- End date of data collection changed to March 31, 2020.
 
7.6.2. Data Collection Method
 
- Data collected dates changed to March 31, 2020.
	
--	--	--	--	---	--

4. MILESTONES

Milestone	Planned date
Study start-up	Request for proposal approval date
Completion of feasibility assessment	Participating institutions and investigators confirmation date
Start of data collection	Site visit training date
End of data collection	March 31, 2020
Final study report	12 months from the last patients

5. RATIONALE AND BACKGROUND

Rheumatoid arthritis (RA) is a chronic inflammatory autoimmune disease that causes joint destruction and leads to loss of function, decreased quality of life [1], and ultimately death [2] from complications. It is characterized by an excessive increase in pro-inflammatory cytokines that causes abnormal inflammation [3]. Therefore, the American Arthritis Foundation has recommended early diagnosis and appropriate treatment targeting maintenance of low disease activity or remission of RA, prevention or delay of joint damage, and recovery of physical abilities and improvement in the quality of life [4].

According to the 2016 Update of the European League Against Rheumatism (EULAR) recommendation, the basic principle of the RA treatment goal is to provide the best care for the patients, and that treatment should be discussed and agreed between the two parties [5]. Therefore, patient evaluation of the treatment is an important factor for its success.

Recently, the development of new treatments with various mechanisms and diagnosis criteria for early detection have allowed diagnosis and treatments in earlier stages of RA than previously possible [6]. However, it is a chronic condition that is still difficult to cure, and various complications [7-10] and decreased quality of life [1] can occur with insufficient treatment or a prolonged disease presence. Within 2 years of diagnosis, irreversible bone erosion has been observed in more than 50% of patients [7], and it was shown that patients with prolonged disease period have a high risk for widespread complications, such as cardiovascular conditions [8], infection [9], and malignant tumor [10].

According to the 2015 American College of Rheumatology Guideline, patients who have insufficient response to or who do not have tolerance to the conventional synthetic disease-modifying antirheumatic drugs (csDMARDs) as the 1st line treatment are recommended to switch to biologic DMARDs (bDMARDs) or the small molecular target therapy JAK suppressor (tofacitinib citrate) to minimize disease activity or to expedite remission [11]. Most patients who receive csDMARDs suffer from a prolonged disease period, and it is important to assess quality of life and treatment satisfaction in this population.

bDMARDs are injectables, and they have been reported to have low compliance [12] owing to invasive administrations and loss of therapeutic effects from immunogenic response [13, 14]. On the contrary, tofacitinib citrate, which has been developed recently and used as an antirheumatic drug, is reported to have similar efficacy [15] and safety [16-18] as those of the bDMARDs and has a higher patient preference owing to its oral route of administration [19].

In a comparison using a RCT, non-inferior effects [15] and safety [20] of tofacitinib citrate were shown when compared to commonly used the bDMARD adalimumab, and both agents showed a higher quality of life than the placebo [21]. However, most clinical treatment success reports compare bDMARDs [22-24], and there are few reports that compare JAK suppressors with bDMARDs and their effects on patient treatment satisfaction and quality of life.

Therefore, the purpose of this study is to compare the two most common clinically used antirheumatic agents, adalimumab and tofacitinib, in terms of treatment satisfaction and quality of life among Korean patients to assess treatment success from patients' perspectives.

6. RESEARCH QUESTION AND OBJECTIVES

This study aim to compare treatment satisfaction and quality of life between patients who have been using tofacitinib citrate and patients who have been using adalimumab for 6 months or more and less than 2 year in treatment of rheumatoid arthritis. The specific objectives are as follows:

Primary objective

To compare the treatment satisfaction between tofacitinib citrate users and adalimumab users.

Secondary objective

To compare the quality of life between tofacitinib citrate users and adalimumab users.

7. RESEARCH METHODS

7.1. Study design

This study is a multi-center, non-interventional cross-sectional study.

7.2. Setting

7.2.1. Study population

The study population is patients with RA who have been using tofacitinib citrate or adalimumab for 6 months or more and less than 2 years in RA treatment at the participating institutions.

7.2.2. Inclusion criteria

Study populations must satisfy the following inclusion criteria for enrollment:

1. ≥ 19 years of age
2. Patients who satisfy the 2010 American College of Rheumatology/European League Against Rheumatism diagnosis criteria ^{a)}
3. Treatment groups:
 - 1) Tofacitinib citrate users: patients who have been taking tofacitinib citrate for more than 6 months
 - 2) Adalimumab users: patients who have been taking adalimumab for more than 6 months
4. Patients who can read and write the questionnaire forms in Korean

7.2.3. Exclusion criteria

Study population who satisfy the exclusion criteria listed below will be excluded from the study:

- 1 Patients who are taking tofacitinib citrate or adalimumab for more than 2 years
- 2 Patients who are taking tofacitinib citrate or adalimumab along with azathioprine or cyclosporine
- 3 Patients who are participating in clinical research with other investigational products
4. Patients who are taking bDMARDs for diseases other than RA

a)

	Score
Target population (Who should be tested?): Patients who	
1) have at least 1 joint with definite clinical synovitis (swelling)*	
2) with the synovitis not better explained by another disease†	
Classification criteria for RA (score-based algorithm: add score of categories A-D; a score of $\geq 6/10$ is needed for classification of a patient as having definite RA)‡	
A. Joint involvement§	
1 large joint¶	0
2 – 10 large joints	1
1 – 3 small joints (with or without involvement of large joints)**	2
4 – 10 small joints (with or without involvement of large joints)	3
> 10 joints (at least 1 small joint)††	5
B. Serology (at least 1 test result is needed for classification)¶¶	
Negative RF and negative ACPA	0
Low-positive RF or low-positive ACPA	2
High-positive RF or high-positive ACPA	3
C. Acute-phase reactants (at least 1 test result is needed for classification)§§	
Normal CRP and normal ESR 0	0
Abnormal CRP or normal ESR 1	1
D. Duration of symptoms¶¶¶	
< 6 weeks	0
≥ 6 weeks	1

*The criteria are aimed at classification of newly presenting patients. In addition, patients with erosive disease typical of rheumatoid arthritis (RA) with a history compatible with prior fulfilment of the 2010 criteria should be classified as having RA.
Patients with long-standing disease, including those whose disease is inactive (with or without treatment) who, based on retrospectively available data, have previously fulfilled the 2010 criteria should be classified as having RA.

†Differential diagnoses differ in patients with different presentations, but may include conditions such as systemic lupus erythematosus, psoriatic arthritis and gout. If it is unclear about the relevant differential diagnoses to consider, an expert rheumatologist should be consulted.

[#]Although patients with a score of less than 6/10 are not classifiable as having RA, their status can be reassessed and the criteria might be fulfilled cumulatively over time.

[§] Joint involvement refers to any swollen or tender joint on examination, which may be confirmed by imaging evidence of synovitis. Distal interphalangeal joints, first carpometacarpal joints and first metatarsophalangeal joints are excluded from assessment. Categories of joint distribution are classified according to the location and number of involved joints, with placement into the highest category possible based on the pattern of joint involvement.

[¶]'Large joints' refers to shoulders, elbows, hips, knees and ankles.

^{**}'Small joints' refers to the metacarpophalangeal joints, proximal interphalangeal joints, second to fifth metatarsophalangeal joints, thumb interphalangeal joints and wrists.

^{††}In this category, at least one of the involved joints must be a small joint; the other joints can include any combination of large and additional small joints, as well as other joints not specifically listed elsewhere (eg, temporomandibular, acromioclavicular, sternoclavicular, etc.).

[#]Negative refers to international unit (IU) values that are less than or equal to the upper limit of normal (ULN) for the laboratory and assay; low-positive refers to IU values that are higher than the ULN but three or less times the ULN for the laboratory and assay; high-positive refers to IU values that are more than three times the ULN for the laboratory and assay. When rheumatoid factor (RF) information is only available as positive or negative, a positive result should be scored as low-positive for RF.

^{§§}Normal/abnormal is determined by local laboratory standards.

^{¶¶}Duration of symptoms refers to patient self-report of the duration of signs or symptoms of synovitis (eg, pain, swelling, tenderness) of joints that are clinically involved at the time of assessment, regardless of treatment status.

ACPA, anti-citrullinated protein antibody; CRP, C-reactive protein; ESR, erythrocyte sedimentation rate.

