## 4 ANALYSIS SETS/POPULATIONS

### 4.1 FULL ANALYSIS SET

All subjects that have satisfied the inclusion criteria and were registered for the study. Inclusion and exclusion criteria are outlined in the study protocol section 7.2.

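### Does the misprinted CRP/ESR row in the RA classification table leave inclusion criterion 2 undefined?

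*Protocol*

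**What the plan says.** Protocol 7.2.2, inclusion criterion 2, admits "Patients who satisfy the 2010 American College of Rheumatology/European League Against Rheumatism diagnosis criteria". Footnote a), which appears after the exclusion criteria in 7.2.3, reproduces the scoring table: four domains are added and 6 of 10 points classify a patient as having definite disease.

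Domain C has two rows. The 0-point row is "Normal CRP and normal ESR 0"; the 1-point row is "Abnormal CRP or normal ESR 1". The domain heading accepts one test result as sufficient. The note to the domain adds only that "Normal/abnormal is determined by local laboratory standards".

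The same footnote says the criteria are meant for newly presenting patients. It adds that patients with long-standing disease, active or not, who on retrospective data "have previously fulfilled the 2010 criteria should be classified as having RA".

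SAP 4.1 defines the full analysis set as "All subjects that have satisfied the inclusion criteria and were registered for the study", and refers back to Protocol 7.2 for the criteria. The SAP does not restate the table.

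**The concern.** A 0/1 item should give every patient exactly one score. Here normal ESR appears in both rows and abnormal ESR in neither, so the rows overlap in one place and leave a gap in another. The 1-point row also credits a normal ESR, which contradicts the 0-point row beside it.

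The table is attached to an eligibility criterion, and membership of the full analysis set depends on meeting the inclusion criteria. A site that scored literally could admit a patient whose CRP and ESR are both normal, or find no score for a patient with normal CRP and raised ESR. Nothing else in either document repairs the row. The rule about placing a patient in the highest possible category is written for joint distribution only. Protocol Table 1 does not list rheumatoid factor, ACPA, symptom-duration category or the total 2010 score, so a misapplication would not show in the collected data.

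**Working it through.** **Step 1: the rows as printed.** The 0-point row needs CRP normal and ESR normal; the 1-point row needs CRP abnormal or ESR normal. For comparison, the last column uses the logical complement of the 0-point row as the 1-point row (CRP abnormal or ESR abnormal).

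| CRP | ESR | Rows met as printed | Rows met with the complement |
|---|---|---|---|
| normal | normal | 0 and 1 | 0 |
| normal | abnormal | none | 1 |
| abnormal | normal | 1 | 1 |
| abnormal | abnormal | 1 | 1 |
| normal | not done | none | none |
| abnormal | not done | 1 | 1 |
| not done | normal | 1 | none |
| not done | abnormal | none | 1 |

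With both tests done, 1 of 4 results is scored twice and 1 of 4 is not scored. The complement removes both faults. It does not settle a single normal result: that matches no row even then, because the 0-point row joins the two tests with 'and'. Domain B is built the same way, with a 0-point row that joins RF and ACPA by 'and' under a heading that accepts one test. That part of the single-test difficulty therefore comes from the table's format. Scoring on whichever test is available is the natural reading.

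**Step 2: when domain C can decide eligibility.** Printed scores: A is 0, 1, 2, 3 or 5; B is 0, 2 or 3; C is 0 or 1; D is 0 or 1. The maximum is 5 + 3 + 1 + 1 = 10, which agrees with the printed denominator. The A, B and D scores form 5 × 3 × 2 = 30 profiles.

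- If A + B + D is 4 or less, one more point gives at most 5, so the patient fails either way.
- If A + B + D is 6 or more, the patient qualifies either way.
- Only A + B + D = 5 is decided by domain C. The profiles (A, B, D) are (1,3,1), (2,2,1), (2,3,0), (3,2,0) and (5,0,0): 5 of 30.
- With symptoms of at least 6 weeks (D = 1), only (1,3,1) and (2,2,1) remain: 2 of 15. The other three have D = 0, which hardly fits current scoring of patients treated for more than 6 months and would matter only when reconstructing the first presentation.

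These are counts of score combinations. The documents give no distribution of patients over them.

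**Step 3: what must coincide for a patient to be affected.** All of the following are needed:

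1. A + B + D = 5.
2. CRP is not abnormal, since an abnormal CRP scores 1 under either wording.
3. The site scores from the printed row rather than from the published criteria that criterion 2 names.
4. Earlier fulfilment of the criteria is not already documented.

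Protocol 7.2.1 also limits the population to patients using one of the two drugs as treatment for rheumatoid arthritis.

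**Step 4: reach into the analysis.** SAP 5.4 takes CRP and ESR as covariates at their recorded values. No endpoint, covariate, sample-size input or model uses the domain C score or the 2010 total. The only link is full analysis set membership.

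**The case for a change.** The strongest argument for acting is that the error is certain, lies in an eligibility rule, works in both directions and cannot be detected from the variables in Table 1, while the correction is a single word. An eligibility rule should be readable without outside help, and a very small effect argues for low priority rather than for leaving the text alone.

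The first part stands: the rows conflict, and text extraction does not readily explain it. The duplicated trailing scores look like a layout effect, but that would not turn one word into its opposite.

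The argument from low cost is weaker. Protocol 8.4 requires prospective ethics approval of amendments, and 7.6.2 names 23 institutions. Data collection ends on 31 March 2020, 19 days after the SAP date of 12 March 2020, so counted from the SAP few enrolments could still benefit. The absence of the score components from Table 1 also means that a corrected row would not by itself alter the analysis set; only review of source charts could do that, and nothing suggests it would find a case. A separate scoring rule for a single available test would add detail to a named instrument without resolving any patient's status that the documents put in doubt.

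**Conclusion.** This is a clerical slip in a reproduced table, and no change to the plan follows. The contradiction affects 2 of the 4 two-test results, and the one point at stake can matter in 5 of 30 score profiles (2 of 15 with symptoms of at least 6 weeks). The intended meaning is plain from the 0-point row, and the criterion itself refers to the published 2010 criteria. Correcting the word would leave every stated number, the TSQM and EQ-5D comparisons and the definition of the analysis set as they are.

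The conclusion rests on two assumptions that the documents support but do not prove: that rheumatology sites apply the named criteria rather than the misprinted row, and that most patients already treated for more than 6 months qualify through earlier fulfilment. If either failed for some patients, the result would be a few doubtful eligibility decisions. Nothing in the documents suggests these would fall more in one drug group than in the other.

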7.3. Variables

The information detailed below will be collected from medical records and patient questionnaires during the study from those who satisfy the inclusion criteria.

Table 1. Evaluation Criteria [15,20-21]

Evaluation Criteria	Information	Evaluation Method
1. Demographics	
• Age• Gender	Medical Chart
	
• Educational level• Financial status• Employment status	Patient Questionnaire
2. Clinical Characteristics	
• Body mass index• Comorbidities• Initial RA diagnosis date• DMARD types used previously• Current use of DMARD (tofacitinib citrate or adalimumab), treatment numbers/duration/doses (mg/month) Co-administered drug types, numbers, dosage (csDMARDs/NSAIDs/steroid; mg/month)• DAS28 components	Medical Chart
3. Treatment Satisfaction	
• Treatment satisfaction questionnaire for medication, (TSQM)	Patient Questionnaire

4. Quality of Life	
• EuroQoL-Visual Analogue Scale, EQ-VAS• EuroQoL-5 Dimensions index, EQ-5D index	Patient Questionnaire
--------------------	---	-----------------------

7.3.1. Propensity score methods

The purpose of the propensity score is to create conditions similar to those of randomized trials by balancing the covariates in subjects between the groups. The propensity score adjustment method reduces multidimensional covariates into a one-dimensional score, or the propensity score. The computed propensity score can be used for bias reduction through restriction, matching, stratification, covariate adjustment, and weighted methods. It can also be used to estimate the mean treatment effect of two groups or the mean treatment effects of the active group compared to those of the control group.

- **Propensity score use of the propensity score in the cross-sectional studies [26-30]**

The propensity score is used in the cross-sectional studies to remove or minimize effects from the disturbance variable. Analytical methods using propensity scores are considered superior to the average covariate analysis method of the one-dimensional study. Therefore, the analytical method using propensity score will be used in this study.

1) *Propensity score matching* [25]

- Propensity score matching can restrict variations between the covariates by matching subjects with similar propensity scores from groups 1 and 2.
- Duplicates not allowed: Once a subject from group 2 is matched with a subject from group 1, he/she cannot be considered for a match to a subject from another group, and therefore, the subject from group 2 can be matched for a maximum of one time.
- Greedy matching (nearest matching method): Subject from group 1 is randomly selected; then the subject with the closest propensity score is selected from group 2 (caliper matching is also an option), and 1:1 matching will be considered.
- If too many subjects are eliminated from the analysis after matching, this method will not be considered as the analytical method, and only the methods described below will be considered and reported. Standards for the decision will be described in the SAP in detail.

2) *Propensity score adjustment* [28]

This method uses all patients enrolled in the study,

- **Propensity score adjustment:** A method for including the treatment variable and the PS itself as a covariate in a multiple model estimating a treatment effect.

3) **Propensity score based weighing** [28]

This method also uses all patient data.

- **Propensity score weighting:** A method of using IPTW (inverse probability of treatment weighting) method to estimate a mean treatment effect of the two drug groups. The weight makes the characteristics of treatment groups similar to the target population.

4) **Propensity score based stratification** [28]

This method also uses all patient data.

- **Propensity score stratification:** A method of stratifying patients according to the quintiles or deciles of their propensity score, and evaluate a treatment effect within each stratum. A pooled treatment effect will then be obtained across strata.

